7.5 Efficacy Analyses

7.5.1 Center pooling

To eliminate potential effect of random fluctuations at small site on the primary endpoints small centers will be pooled. A study center will be pooled if it doesn't meet both of the following conditions:

- It has at least 10 patients in the PP population;
- It has at least one patient in each treatment group in the PP population.

The smallest center that does not meet the above requirements will be pooled with the next smallest center. The procedure will be repeated until all pooled centers meet the above two requirements.

Pooled center will be used in all the efficacy analyses.

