7.5.2.1 Analysis of clinical equivalence of test and reference treatments

To show the clinical equivalence, estimates of mean percent change from Baseline in the inflammatory lesion count will be calculated for the Test and Reference treatment, and then the 90% CI for the mean ratio will be constructed using Fieller's method. Bioequivalence will be established if the 90% confidence interval for the ratio of Test/Reference means is contained within the interval [0.80, 1.25] for the PP population.

To this end, first an ANOVA model will be fit with percent change from Baseline in lesion count as outcome and treatment, center and treatment-by-center interaction, as factors on the data from Test and Reference treatments only (excluding Vehicle patients). If the treatment-by-center interaction factor is not significant at the 0.05 level, the model will be rerun without the interaction term. Treatment means and standard errors will be estimated from this model.

Then Fieller's formula will be applied; covariance between the treatment means will be assumed to be 0. See [Appendix 11.4](#) for complete description of the Fieller's formula.

A non-parametric rank based ANOVA will be considered when the data is highly skewed. The evaluation of skewness, (using SAS® PROC UNIVARIATE) will be performed using the residuals from ANOVA and if the skewness statistic is less than -2 or greater than +2, the analysis will be performed on the ranks of the percent change in the inflammatory lesion count values.

Analysis of bioequivalence will be performed both on the PP population and on the mITT population. The results on the PP population will be considered definitive and the results on the mITT population will be considered supportive.

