In the case of this study the two samples are independent (different patients), thus covariance can be assumed to be zero, and the formula simplifies to:

$$(m_L, m_U) = \frac{1}{1-g} \left[\frac{m_t}{m_r} \mp \frac{t_{r,\alpha}}{m_r} \sqrt{s e_t^2 + \frac{m_t^2}{m_r^2} s e_r^2 - g \cdot s e_t^2} \right]$$

where

$$g = \frac{t_{r,\alpha}^2 s e_r^2}{m_r^2}$$

Here m_t and $s e_t$ are mean and standard error estimate for test treatment and m_r and $s e_r$ for reference treatment correspondingly obtained from the above model. The degrees of freedom r can be obtained from the model as degrees of freedom for the error term in the overall ANOVA table, $\alpha = 0.05$ (for the 90% confidence interval). The term $t_{r,\alpha}$ can be calculated in SAS as $\text{tinv}(\alpha, r)$.

Clinical equivalence analysis in secondary endpoint

```
proc freq data=<dataset>
  tables <treatment>*<success> / riskdiffc;
run;
```

Note: this analysis needs to be performed on a dataset containing test and reference treatment patients only.

Evaluation of skewness

This evaluation will be performed on the residuals output by the "output" statement in PROCGLM above:

```
proc univariate data=residuals;
  var residual;
run;
```

Non-parameteric rank ANOVA

If decision to use the rank ANOVA is taken, the data will be ranked first:

```
proc rank data=<dataset>
  var <change_from_baseline>;
  ranks rank;
run;
```

After that the analysis will proceed using the same SAS code as described above but using rank variable instead of the original change from baseline.

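### If residual skewness falls outside -2 to +2, the primary equivalence test moves to ranks without a margin of its own, and [0.80, 1.25] then no longer bounds the ratio of mean percent changes

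*SAP*

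**What the plan says.** SAP 7.5.2.1 fits an ANOVA with "treatment, center and treatment-by-center interaction, as factors on the data from Test and Reference treatments only", drops the interaction if it is not significant at 0.05, and puts the two treatment means into Fieller's formula. Equivalence is met if the 90% interval for the ratio of mean percent changes is "contained within the interval [0.80, 1.25] for the PP population". SAP section 5 and the protocol synopsis give the same criterion.

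The section then adds a switch: "A non-parametric rank based ANOVA will be considered when the data is highly skewed". The switch has a numeric trigger. If the skewness of the ANOVA residuals is below -2 or above +2, "the analysis will be performed on the ranks of the percent change in the inflammatory lesion count values". Protocol 12.5.1 applies it to both the equivalence and the superiority evaluations.

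SAP 11.4 gives the mechanics: "If decision to use the rank ANOVA is taken, the data will be ranked first", and then "the analysis will proceed using the same SAS code as described above but using rank variable instead of the original change from baseline".

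[0.80, 1.25] is the only primary equivalence margin in either document. Neither says what a ratio of mean ranks estimates, what range of it is acceptable, or how a rank result supports a conclusion about mean percent change.

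**The concern.** A superiority test can move to ranks without difficulty, because its null hypothesis of no difference needs no margin. An equivalence test cannot. Its margin is a number on a particular scale, and 0.80 on the scale of mean percent change is not 0.80 on the scale of mean ranks.

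The switch governs the PP analysis that the SAP calls definitive for equivalence. If it fires, the trial decides on a different quantity from the one in its hypothesis, and nothing holds the error near 5% at the stated boundary. A product at a true ratio of 0.80 could pass much too often, or a good product could be judged by a stricter or looser standard than intended. Which of these happens depends on a distribution that the documents do not describe.

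**Working it through.** **Inputs.** From the documents: 1:1:1 allocation, 224 PP and 280 mITT patients per arm, reductions of 55% (Reference) and 40% (Vehicle), SD below 47 (SAP 3.1 and 3.2); margin and trigger (SAP 7.5.2.1); about 26 centers (protocol synopsis). Distribution shapes are assumptions.

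**The plan's own figure.** The stated power is redacted and cannot be reproduced. From the plan's inputs (SD 47, true ratio 1, normal data, no center term), Fieller equivalence power at 224 per arm is about 0.72, each superiority test at 280 per arm has 0.965, and the joint probability is about 0.69.

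**What the margin means on ranks.** Let p = P(Test better) + 0.5 × P(equal). With n patients per arm:

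- mean rank of Test = n·p + (n+1)/2
- the two mean ranks sum to 2n+1
- for large n, the ratio of mean ranks = (0.5 + p)/(1.5 - p)

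Ratio 0.80: 0.5 + p = 1.2 - 0.8p, so p = 0.7/1.8 = 0.389. Ratio 1.25: 0.5 + p = 1.875 - 1.25p, so p = 1.375/2.25 = 0.611. At n = 224 the lower limit is (0.8/1.8 × 449 - 112.5)/224 = 0.3886, and the upper is 0.6114. No distributional assumption enters. Reversing the rank direction inverts the ratio, but the interval is its own reciprocal, so the decision is unchanged.

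**Where a true ratio of 0.80 falls.** Take remaining lesions as a percentage of baseline: Reference mean 45, Test mean 100 - 0.80 × 55 = 56. For lognormal data the log variance is ln(1 + SD²/mean²) and the log mean is ln(mean) minus half of that.

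- SD 47 (Test) and 37.8 (Reference): log means 3.759 and 3.540, log variances 0.533 and 0.534. p = Φ(-0.219/√1.067) = 0.416, so the rank ratio is 0.916/1.084 = 0.845. A product on the boundary lies inside the rank interval. The rank limit of 0.80 is reached at a true ratio of 0.75.
- SD 47 in both arms: log means 3.759 and 3.438, log variances 0.533 and 0.738. p = Φ(-0.321/√1.271) = 0.388, rank ratio 0.80. The two boundaries happen to coincide.
- Arms that differ only in the share of worsening patients (most near 41, the rest near 160; share 12.6% Test, 3.4% Reference). If the clusters do not overlap, p = 0.874 × 0.034 + 0.5 × (0.874 × 0.966 + 0.126 × 0.034) = 0.454, rank ratio 0.954/1.046 = 0.91.

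**Simulated pass rates at a true ratio of 0.80.** There were 20,000 trials per cell, with 26 centers of 8-9 PP patients per arm, the treatment and center model, and the interaction kept if p < 0.05. Whole trial means equivalence plus both superiority tests.

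| Assumed shape (SD Test/Reference) | Trigger fires | Equivalence: SAP rule | Equivalence: Fieller | Whole trial: SAP rule | Whole trial: Fieller |
|---|---|---|---|---|---|
| Lesion counts, same CV (42/34) | 1.0% | 6.1% | 5.7% | 3.5% | 3.5% |
| Lesion counts, similar SD (43/42) | 3.0% | 5.2% | 5.0% | 3.1% | 3.0% |
| Gamma, common SD 47 | 13% | 5.5% | 4.8% | 3.3% | 3.0% |
| Lognormal, common SD 47 | 84% | 4.5% | 4.7% | 2.9% | 3.1% |
| Gamma, same CV | 6% | 8.6% | 6.0% | 3.7% | 3.4% |
| Lognormal, same CV (47/37.8) | 73% | 21% | 6.1% | about 7% | about 3% |
| Lognormal, shifted | 93% | 1.3% | 4.9% | 1.2% | 4.2% |
| Worsening share (42/26) | 58% | 49% | 6.6% | 14.5% | 4.0% |

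The whole-trial lognormal same-CV run used SDs of 43.9, 35.2 and 47 (Vehicle). Count cells used baselines uniform on 8-50.

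**At a true ratio of 1**, apparent equivalence power under the SAP rule against Fieller is 0.98 against 0.71 (lognormal, SD 47), 0.80 against 0.71 (gamma, SD 47) and 0.98 against 0.95 (lognormal, SD 35).

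**The case against.** The strongest reply is that the documents never say [0.80, 1.25] applies to mean ranks. The rank ANOVA is only to be considered, and the defect is an omission. The first part is true, but the text goes on to say the rank analysis will be performed once a numeric limit is crossed, with the same code, and no other criterion exists. If the margin does not carry over, that branch has no equivalence criterion at all. Either reading needs correcting.

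Second, in the models closest to the documents (lesion counts with the 8-50 entry range) the trigger rarely fires and the error hardly moves. That stands. The large figures come from assumed shapes and are not a forecast.

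Third, Fieller is not exact either: it gives 6.1% and 6.6% in two cells above, and about 7% at a true ratio of 1.25 when the Test SD is below the Reference SD. In some cells it gives a higher error than the SAP rule, such as the shifted lognormal. Also true, but there the SAP rule has a lower error only because it tests something else; at 1.25 in same-CV cells it gives 3.4% (lognormal) and 13.4% (gamma). Specifying and justifying a rank-scale margin is a possible alternative, but it would change what the trial claims to show.

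Three refinements also stand: ties count one half; the 0.389-0.611 range is approximate for center-adjusted means or unequal arms (0.390 to 0.613 with 200 Test and 248 Reference patients); and a bootstrap of unadjusted means may differ from Fieller through center weighting as well as skewness.

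**Conclusion.** The concern holds. As written, crossing the skewness limit replaces the ratio of mean percent changes with a ratio of mean ranks in the definitive equivalence analysis and supplies no margin for it. Carried over, [0.80, 1.25] bounds the probability of a better Test result at about 0.39 to 0.61. That result is algebra and needs only near-equal arms.

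The effect on error is not determined by the documents. At a true ratio of 0.80 it can rise, fall or stay put, and the chance that the trigger fires is unknown. Requiring superiority over Vehicle as well reduces the trial-level error but does not restore the intended quantity. The simulated values rest on assumed shapes, and other shapes could fall outside them. This should be fixed before unblinding.

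**What to change.** Replace the rank sentence for equivalence with wording such as:

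> The equivalence decision is based on the Fieller 90% CI for the ratio of mean percent change, whatever the residual skewness. If skewness is outside -2 to +2, a bootstrap percentile 90% CI for the ratio of unadjusted arm means (patients resampled within treatment arm only, 2,000 resamples, seed fixed before unblinding) is compared with [0.80, 1.25] and reported as a sensitivity analysis. The decision rests on Fieller and any disagreement is reported. Rank ANOVA is used for the superiority tests only, when skewness is outside -2 to +2.

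Do not resample within center. The pooling rule in SAP 7.5.1 keeps a center once "It has at least 10 patients in the PP population" and "It has at least one patient in each treatment group in the PP population", and such small cells understate the variance. At a true ratio of 0.80, resampling within arm and center raised the bootstrap error from 6.1% to 7.2% (lognormal, same CV) and from 5.3% to 6.6% (lognormal, common SD).

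Align SAP 5, 7.5.2.1, 7.5.2.2 and 11.4 with the protocol synopsis and 12.5.1. If the protocol is not amended, record the change in SAP section 8, which now reports none. As a separate drafting correction, the PROC RANK placeholder in SAP 11.4 should name percent change, as 7.5.2.1 does.

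The cost is wording and a short program. The real loss is the protocol's non-parametric route for equivalence, and with it the higher apparent power: at SD 47 and a true ratio of 1, equivalence power is about 0.71 (bootstrap 0.69 to 0.71). In lognormal data Fieller and bootstrap decisions disagreed in 0.5-0.8% of trials at a ratio of 0.80 and in 3% at a ratio of 1 with SD 47.

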7.5.2.2 Analysis of superiority to vehicle control

The analysis of superiority will be performed separately for the Test treatment versus the Vehicle treatment and for the Reference treatment versus the Vehicle treatment. Each of these analyses will be performed using an ANOVA model with percent change from baseline in the lesion count as outcome and treatment, center and treatment-by-center interaction as factors. If the treatment-by-center interaction factor is not significant at the 0.05 level, the model will be rerun without the interaction term. The model will be fit on data from the Test and Vehicle treatment for analysis of superiority of the Test treatment and separately on data from the Reference and Vehicle treatment for analysis of superiority of the Reference treatment. From this model, the least square (LS) mean estimate for each treatment group with the 95% CI will be calculated; further, an estimate of the LS mean difference between the active treatment (Test or Reference) and Vehicle with 95% CI and the p-value for test of no difference will be calculated.

Superiority will be established if the mean percent change from Baseline (reduction) for each active treatment is estimated to be greater than, and statistically significantly different from ($p < 0.05$ for test of no difference) that for the Vehicle, for the mITT population.

Analysis of superiority will be performed both on the PP population and on the mITT population. The results on the mITT population will be considered definitive and the results on the PP population supportive.

A non-parametric rank based ANOVA will be considered under the same circumstances as for the analysis of bioequivalence.

7.5.3 Analyses of Secondary Endpoint Outcome

The secondary endpoint is the IGE score (see [Appendix 11.2](#)), expressed in terms of treatment success or failure. Success is defined as an IGE score at Week 12 of 0 (clear) or 1 (almost clear). Any other outcome will be considered a failure. Patients who are discontinued prematurely from the study due to lack of treatment effect after at least 8 weeks of compliant treatment will be considered as treatment failures both in the PP and mITT analyses. Patients who do not have a valid Week 12 assessment for any other reason will be excluded from the PP analysis, but included in the mITT analysis using LOCF approach to impute the response.

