Data Sets to be Analyzed:	
Three patient populations are defined as follows:
 
 1. The Safety Population includes any patient who was randomized in the study and had at least one dose of Investigational product. 2. The Modified Intent-to-Treat (mITT) Population includes all randomized patients who met all inclusion/exclusion criteria, received study treatment, and returned for at least one post-baseline visit with lesion count. 3. The Per-Protocol (PP) Population includes all randomized patients who met all inclusion/exclusion criteria, were compliant with the assigned study treatment (who applied 75% to 125% of the scheduled applications), returned to the study site for the primary endpoint visit (12 week evaluation) within +/- 4 days OR discontinued from the study as a treatment failure and did not have any protocol violations. 4. Patients who are discontinued early from the study due to lack of treatment effect after completing at least eight weeks of treatment will be included in the mITT and PP population as treatment failures (i.e., non-responders) and the change in inflammatory lesion count from the baseline visit to the last completed visit prior to discontinuation due to lack of efficacy will be carried forward in the primary endpoint analysis. In addition, patients whose condition worsens after completing at least eight weeks of treatment and require alternate or supplemental therapy for the treatment of facial rosacea during the study will be discontinued, included in the PP population analysis, and provided with effective treatment. A last observation carried forward (LOCF) approach will be used for imputing missing efficacy results in these PP patients and they will be considered as failures in the IGE evaluations. 
Patients discontinued prematurely for other reasons will be excluded from the PP population, but included in the mITT population, for which missing efficacy data will be imputed using LOCF.
 
For the purpose of determining the per-protocol status of the patient, a “protocol violation” is any patient or investigator activity that could have
			

	
possibly interfered with the therapeutic administration of the treatment or the precise evaluation of treatment efficacy.
 
Efficacy analyses will be performed on the mITT and per-protocol populations. All efficacy data will be listed by treatment and patient in data listings.

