11.3.4 Patient Discontinuation Criteria

Investigators are urged to enroll only those eligible patients who are likely to complete the entire study and who are willing to comply with the protocol-specified procedures. It is the right and duty of the investigator to interrupt the treatment of any patient whose safety and well-being are determined to be at risk, or who may be experiencing unmanageable factors that may interfere with the study procedures and/or the interpretation of study results. Such patients should be withdrawn from the study rather than continued under a modified regimen.

Discontinuation is permanent; once a patient is discontinued, he/she shall not be allowed to enroll again.

A patient may be discontinued from the study for any of the following reasons:

1. Patient decision/withdrawal of consent;
2. Adverse event, including intercurrent illness, which required study discontinuation;
3. If the patient's condition has worsened to the degree that the Principal Investigator feels it is unsafe for the patient to continue in the study;
4. If the patient's drug code is unblinded;
5. Insufficient therapeutic response (after at least 8 weeks of compliant treatment);
6. If a patient misses more than 6 consecutive doses;
7. If the subject misses more than 1 required visit;
8. Significant protocol violation;
9. If the patient is lost to follow-up;
10. If the patient becomes pregnant;
11. If the patient becomes a prisoner or becomes involuntarily incarcerated;
12. Any other reason that may affect the outcome of the study or the safety of patients; or
13. Termination of the study by the Sponsor.

A patient that discontinues from the study will not be replaced.

A significant protocol violation is defined as any patient or Investigator activity that could have possibly interfered with the therapeutic administration of the treatment or the precise evaluation of treatment efficacy.

The reasons for a patient discontinuation will be documented. If a patient is discontinued from the study for any reason, the procedures scheduled for Visit 4 will be completed and any outstanding data and study drug should be collected, if possible. Information, in addition to the reason for discontinuation and the date of removal, will be documented on the Electronic Case Report Form (eCRF).

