12.4.4 Datasets to be Analyzed

Three analysis populations will be used in the analysis of the clinical data and they are defined as follows:

1. The Safety population includes any individual who was randomized into the study and used at least one dose of Investigational Product.
2. The mITT population includes all randomized patients who met all inclusion/exclusion criteria, received study treatment, and returned for at least one post-baseline visit with lesion count.
3. The PP population includes all randomized patients who met all inclusion/exclusion criteria, were compliant with the assigned study treatment (who applied 75% to 125% of the scheduled applications), returned to the study site for the primary endpoint visit (12 week evaluation) within +/- 4 days OR discontinued from the study as a treatment failure (after completing at least 8 weeks of compliant study medication use), and did not have any protocol violations. The compliance will be verified by the use of patient diaries. Patients who are discontinued early from the study due to lack of treatment effect, or who require alternate or supplemental therapy to treat their rosacea, after completing at least eight weeks of treatment will be included in the mITT and PP population as treatment failures on the IGE and their change in inflammatory lesion count from baseline to the last completed visit prior to discontinuation will be carried forward (LOCF).

Patients discontinued prematurely for other reasons will be excluded from the PP population, but included in the mITT population, with missing efficacy data imputed using LOCF.

For the purpose of determining the per-protocol status of the patient, a “protocol violation” is any patient or investigator activity that could have possibly interfered with the therapeutic administration of the treatment or the precise evaluation of treatment efficacy.

Efficacy analyses will be performed on the mITT and Per-protocol populations.

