6.3 Per Protocol Population (PP Population)

The PP population includes all mITT patients who apply 75% to 125% of the scheduled applications of the assigned product for 12 weeks, do not miss more than 6 consecutive applications, return for the 12-week evaluation within +/- 4 days OR have discontinued from the study due to lack of treatment effect (after completing at least 8 weeks of compliant study medication use), and have no protocol major violations.

Patients who are discontinued prematurely from the study due to lack of treatment effect after completing at least 8 weeks of compliant study medication use and without major protocol violations will be included in the PP population as treatment failures (i.e., non-responders) even if they do not have Week 12 evaluation within the visit window or at all. An LOCF approach will be used for imputing missing lesion counts in these PP patients and they will be considered as failures in the IGE evaluations.

Patients discontinued prematurely for other reasons (including those who discontinue due to lack of treatment effect with less than 8 weeks of treatment) will be excluded from the PP population, but included in the mITT population, using LOCF.

Patients can be additionally excluded from the PP population due to non-compliance, if the Investigator's and Sponsor's review of their dosing times suggests a clinically meaningful departure from a twice-daily dosing pattern.

For the purpose of determining the PP status of the patient, a "major protocol violation" is any patient or investigator activity that could have possibly interfered with the therapeutic administration of the treatment or the precise evaluation of the treatment efficacy.

The PP population will be considered as definitive for testing the clinical equivalence and as supportive while testing the superiority.

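### SAP 7.5.3 and 6.3 omit one of the two IGE-failure triggers in Protocol 12.4.4 (needing other rosacea therapy after eight weeks), and SAP 8 declares no change

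*SAP*

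**What the plan says.** Protocol 12.4.4 joins two conditions with an *or*. The first is early discontinuation for lack of treatment effect. The second covers patients "who require alternate or supplemental therapy to treat their rosacea, after completing at least eight weeks of treatment will be included in the mITT". The same sentence names PP as well, and it makes these patients treatment failures on the IGE. Their lesion counts are carried forward.

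The protocol synopsis (Data Sets to be Analyzed) describes the second group in a sentence of its own, as "patients whose condition worsens after completing at least eight weeks of treatment and require alternate or supplemental therapy for the treatment of facial rosacea". It says that they will be discontinued and kept in the PP analysis, and that "they will be considered as failures in the IGE evaluations".

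SAP 7.5.3 sets failure on one condition only, for patients "discontinued prematurely from the study due to lack of treatment effect after at least 8 weeks of compliant treatment will be considered as treatment failures", in both PP and mITT. Anyone without a valid Week 12 assessment for another reason leaves PP but is "included in the mITT analysis using LOCF approach to impute the response".

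SAP 6.3 makes its PP exception for one group: "Patients who are discontinued prematurely from the study due to lack of treatment effect after completing at least 8 weeks of compliant study medication use". The PP carry-forward rule in SAP 7.5.2 is restricted in the same way. SAP 8 states that nothing departs from the protocol-specified analyses.

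**The concern.** A failure rule should follow the clinical event that the protocol names. Under SAP 7.5.3 it follows the discontinuation reason that the site records. Protocol 11.3.4 lists insufficient response (item 5) separately from worsening (item 3: "If the patient's condition has worsened to the degree that the Principal Investigator feels it is unsafe" to continue). A patient who needs other rosacea therapy after eight weeks can therefore properly be recorded under a reason other than lack of effect.

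Two analyses are touched. SAP 7.5.3.2 makes mITT definitive for IGE superiority over vehicle, and there the patient's score comes from carry-forward instead of being fixed as failure. PP is definitive for equivalence, and there the SAP removes a patient whom the protocol retains. Because SAP 8 declares no change, the programmer has two conflicting rules and no statement of which one governs.

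**Working it through.** The plan states no figure for this rule, so there is none to reproduce. The check is a comparison of the texts, followed by a scale for the effect.

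**1. The rules side by side.** Take a patient withdrawn after at least eight weeks because other rosacea therapy is needed, with worsening as the recorded reason.

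| Item | Protocol 12.4.4 | SAP |
|---|---|---|
| IGE in mITT | Failure | Last IGE carried forward (7.5.3) |
| PP membership | Kept, as IGE failure | Excluded (6.3, 7.5.3) |
| Lesion count in mITT | Carried forward | Carried forward (7.5.2) |
| Lesion count in PP | Carried forward | Not used, patient excluded (6.3, 7.5.2) |

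Three of the four rows differ. The mITT lesion count, which is the basis of the primary superiority test, does not.

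**2. When the mITT score actually changes.** Any IGE other than 0 or 1 is a failure. The two rules therefore give different scores only if the carried-forward IGE is 0 or 1. The patient entered at IGE 3 (inclusion criterion 6) and needed other treatment. Protocol 11.3.4 asks for the Visit 4 procedures at withdrawal if possible, and 11.7.4 includes the IGE among them. A carried-forward 0 or 1 would mainly need a good score at the previous visit, a later flare, and no IGE at withdrawal.

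**3. Scale in mITT.** With the planned 280 per arm, one patient scored success instead of failure moves that arm by 1/280 = 0.36 percentage points.

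As an illustration only, assume the following, none of which is in the documents:
- vehicle success of 15-25% and active success of 25-35%;
- affected patients (vehicle, active) of (0, 0), (3, 3), (8, 3) or (8, 8);
- a last IGE of 0 or 1 in 10% or 30% of them, rounded to whole patients.

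The largest shift in the active-minus-vehicle difference is one net patient, 0.36 points. Two-sided Fisher tests for the (8, 3) case at 30%, which adds 2 vehicle and 1 active success:

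| Active vs vehicle successes of 280, failure rule | p | With carry-forward | p |
|---|---|---|---|
| 70 vs 42 | 0.0042 | 71 vs 44 | 0.0064 |
| 84 vs 56 | 0.0083 | 85 vs 58 | 0.0116 |
| 98 vs 70 | 0.0127 | 99 vs 72 | 0.0169 |
| 90 vs 70 | 0.0753 | 91 vs 72 | 0.0939 |

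No scenario crossed 0.05.

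**4. Scale in PP.** Restoring one IGE failure to an arm of 224 with success rate p lowers that rate by p - 224p/225 = p/225. For an assumed p of 25-35% this is 0.11-0.16 points, against an equivalence margin of 20 points. For the lesion count, restoring one patient with an assumed zero percent change to an arm averaging the planned 55% reduction lowers the mean by 55/225 = 0.24 points. If that arm is Test, the ratio falls by 1/225 = 0.4%. A patient whose count rose above baseline would move it somewhat more.

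**The case against.** **Needing other therapy is simply lack of effect, so the SAP is using shorthand.** That may be the intent, but the protocol keeps the two apart: by the *or* in 12.4.4, by a separate sentence in the synopsis, and by separate items in 11.3.4. SAP 3.1 does say that a patient who worsens to an unsafe degree may be discontinued as a treatment failure. This weakens worsening as the example, but it is permissive overview text and sets no score.

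**Only 12.4.4 extends the rule to mITT.** True. The synopsis ties the second-trigger failure rule to PP patients. But 12.4.4 is the protocol's full definition of the analysis sets, it names both populations, and the synopsis does not contradict it.

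**The score will almost never change.** This largely stands, for the reasons in step 2 of the working, and it sets the size of the point.

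A reader might infer more than the documents support:
- *That rescued patients stay in and are scored on a post-rescue Week 12 IGE.* The synopsis says these patients will be discontinued. Protocol 11.3.5 leaves disqualification after prohibited treatment to case-by-case consultation, but retaining a patient who needed rescue would go against the synopsis. It would be a conduct deviation, not a planned route.
- *That superiority power is materially reduced.* That needs several net vehicle patients who required rescue and still carried forward a 0 or 1. Nothing in the documents suggests this.
- *That a false superiority claim is at risk.* If rescue is commoner on vehicle, carry-forward would narrow the difference from vehicle, not widen it.

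**Conclusion.** The discrepancy is real and undeclared. SAP 7.5.3 and 6.3, with the PP rule in 7.5.2, omit a failure trigger that Protocol 12.4.4 states for both mITT and PP. For a patient withdrawn after eight weeks to receive other rosacea therapy, and recorded under a reason other than lack of effect, the mITT IGE is carried forward instead of set to failure, and the patient leaves PP instead of staying as a failure.

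The effect is probably very small: 0.36 percentage points for each mITT patient whose score changes, with few such patients expected, on a supportive secondary endpoint. That judgement assumes that need for rescue is uncommon and that most such patients have a last IGE of 2 or more. The documents give no rescue or IGE success rates that would test either assumption, so no power loss can be claimed. The case for acting is that the rule should be unambiguous before unblinding and that the correction is cheap.

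**What to change.** - **SAP 7.5.3:** extend the treatment-failure sentence with the protocol's second condition, for example *or who need alternate or supplemental therapy for their rosacea after at least 8 weeks of treatment*.
- **SAP 6.3 and the PP carry-forward rule in 7.5.2:** add the same clause, so that PP membership and lesion-count handling match 12.4.4. For this to take effect, the missed-Visit-4 deviation (SAP 7.4, item 9), which exempts only lack of effect, needs the same exemption. The prohibited-medication deviation (item 1) should not remove these patients from PP because of the therapy that defines the trigger.
- **Alternatively:** if the narrower rule is intended, declare and justify it in SAP 8.

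No new lesion-count rule is needed for patients who are not withdrawn, since neither document provides for them. The cost is one clause in each place. Medication start and stop dates and reasons for use are already collected under Protocol 11.5.4, so no new data are required.
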